In between study sessions, and as part of the Stanley-Brown Safety Plan, some enrolled participants will be able to call or text the PI ([name], CoI 1 or any accredited mental health professional) on a cellphone if they feel that the measures in the safety plan are ineffective and they are in impending danger of attempting suicide. Families, parents, caregivers, and participants will be encouraged to save the emergency study phones as “**Emergency Teen Brain Training**” in their mobile devices so that they can easily reach us. The PI and accredited mental health professionals will save the participants number on their cellphone as “TBT-participant ID” (after consent and assent forms are signed) in order to be able to know who is calling and quickly respond. The participant would only be identifiable by ID number and no names would be linked to the participants’ phone numbers on personal cell phone devices. Participants and their parents will be told that emergency phone calls/texts will be returned by the PI or the psychologist/psychiatrist within **1 hour** (as the PI, accredited mental health professionals and/or psychologist/psychiatrist may be providing services to other patients); or as soon as the study staff can alert those clinicians or “on call” staffing accredited mental health professionals, of a participant’s suicide attempts risks; whichever time frame is shorter. Participants and their parents will be informed of such procedures in the consent and assent form.

However, if the calls, emails, or text are received during the night hours (e.g., after 9 pm) calls/text will not be answered until the next day, and they should call 911 or go to the nearest emergency room to keep themselves safe.

[figure not shown]

Figure 1: Adapted from Labouliere et al. (2018). This figure provides general guidance for clinicians in charge of at-risk participants. Procedures within a research project are different from some of the assumed timing in this figure because the programmed contact times during the research are different from an ongoing standard clinical practice (i.e., weekly psychotherapy or medication appointments). This plan, however, provides good general guidance for research staff to interact and assess participants' safety while actively enrolled in research.

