1. **Safety Plan:** Able to cooperate with the (Stanley & Brown, 2012) Safety Plan. Additional positive criteria include details and accessibility of means and persons to enact it. Participants should be able to provide the name of an adult that they can contact if suicide ideation escalates. Additionally, participants should be able to name specific activities or de-escalating regulatory actions to cope with elevated suicide ideation. The credibility of the suicide plan is often indicated by levels of specificity and elaborations in the coping strategies provided. Evaluating a safety plan specificity is a subjective judgment, therefore the ability to cooperate to create a plan is more important than its level of detail as the latter may depend on verbal and communication skills that do not indicate willingness or ability to follow a safety plan.

2. **C-SSRS:** Any suicide ideation severity yielded by the (C-SSRS, ⁴⁹), Scores 0-5-.

Category 0 – Absent suicide ideation or attempts
 Category 1 – Wish to be Dead
 Category 2 – Non-specific Active Suicidal Thoughts
 Category 3 – Active Suicidal Ideation with Any Methods (Not Plan) without Intent to Act
 Category 4 – Active Suicidal Ideation with Some Intent to Act, without Specific Plan

Category 5 – Active Suicidal Ideation with Specific Plan and Intent
 Category 6 – Preparatory Acts or Behavior
 Category 7 – Aborted Attempt
 Category 8 – Interrupted Attempt
 Category 9 – Actual Attempt (non-fatal).
Category 10–Completed Attempt (fatal)

3. **Caregivers/parents or adult participants statement of responsibility:** If C-SSRS yields scores of 4 or 5 or higher but parents or caregivers or adult participants state that they can keep the participants safe at home.

4. **Participants statement:** Participants can commit to not attempting suicide between the present and the next research encounter.

5. **Suicide means and psychoeducation.** Low to moderate risks during evaluation of access to suicide means.

6. **Recommendation to parents** and additional measures to ensure safety of enrolled participants

- Caregiver(s) will be recommended to increase the level of care with existing providers or seek them if currently absent. Referrals to the U of M outpatient clinic will be provided to the participants and the caregiver.

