- [name] (or the designated psychiatrist or accredited mental health professional) will increase contact with participants/family (call and talk to participants 1 or 2 times a week as needed), particularly if staff becomes aware of periods of high stress, family chaos, increased difficulties at school, bullying, losses, or transitions in care.

- **Document:** risk and protective factors assessment, safety plans, rationale for level of intervention/care.
- When in doubt – consult [name] or the designated pediatric psychiatrist.
- Consult with other providers in the department of psychiatry

7. The Dialectical Behavioral Therapy (DBT: [contact]) team can be consulted via email 2 weeks before the visit with copy to the PI: [contact]

16.5 Exclusion and triage of in person suicide risks. Risk factors are cumulative, the presence of one risk factor does not automatically exclude a participant. The presence of many risk factors and the absence of protective factors, however, merits considering exclusion from the research.

Exclusion and referral for increased outpatient level of care or emergency department (ED) assessment for hospitalization if:

- Scores of **4 or 5** or higher in the C-SSRS (Category 4 - 6) and:
 - **Caregivers are unable or unwilling to keep the participants safe at home.**
 - Participants show uncertainty (i.e., cannot promise not to attempt suicide) about not attempting suicide between the present and the next research session.
- Inability to fashion a credible Stanley & Brown Safety Plan.

[figure not shown]
- Determination of high chronic or acute risk due to presence of multiple risk factors and absence of protective factors: e.g., access to suicide means and unreliable or absent control over them.
- In consultation with the “on call” PI or pediatric psychologist this could result in referral for increased levels of current established care or escorting the participants and family to the emergency department (ED) at the U of M.
- Personnel will be trained to conduct and document a safety plan and interview. **The IMM and the PI will review the safety plans after the conclusion of the 1st main interview.**

[figure not shown]

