16.6 Suicide Risk Assessment Remote Participants

- Before the remote meeting, ensure staff has the correct email address and phone number for both the adolescent and the caregivers and other emergency contacts by calling and emailing them 2 weeks in advance of the remote research section **Participants and their parents/caregivers will program the study phone numbers and emails in their cellphones**. This will be necessary to send the **Zoom** or other video platform invitation in advance of the visit. Zoom or videoconferencing must be videotaped/recorded for purposes of training, diagnosis, and reliability coding of symptoms among the staff members.
 - The Dialectical Behavioral Therapy (DBT) team can be consulted via email two weeks before a scheduled remote assessment or testing session ([contact]) with copy to the PI: [contact].
- Verify adolescent’s location at the beginning of every remote session to ensure emergency services can be deployed if necessary. Obtain the current specific address and location
- Once the remote session starts. Confirm phone number, email and emergency contacts are accurate and accessible.
- Ensure the adolescent is in a reasonably private and safe environment.
- Ensure the caregiver is in the home or readily accessible via phone or text.
- Ensure participants and caregivers can contact research staff easily. If technology issues arise, give them your easiest access number and request/verify theirs and their emergency contact/caregiver’s contacts.
- **Use the same guidelines and instruments as the in-person suicide risk assessment.**
- **Lower-level interventions that can be used for C-SSRS scores 1-3:**
 - National Suicide Prevention Lifeline: [name]
 - Crisis Text Line: Text “Home” to 741741
 - Virtual Hope Box (app store)
 - Collaborative brainstorming with participants and caregivers to develop/review safety plan.

16.7 Exclusion and management of remote suicide risks.

- **If a participant cannot maintain safety or if staff determines that safety cannot be maintained:**
 - Caregiver should be contacted and directed to call 911 and/or go to the nearest Emergency Room (ER)
 - If the caregiver is absent or unreachable, research staff can call 911 and direct emergency responders to the participants’ location.
 - **Text, email, zoom, skype, or use any possible means of communication to call staffing “on call” PI or pediatric psychiatrist/clinical before taking the step of calling 911 on the participants’ behalf.**

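### Section 16.3 offers some participants in impending suicidal danger a call-back within 1 hour, but gives its 911/emergency-room instruction only for a night window with no stated end.

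*Combined protocol and SAP*

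**What the plan says.** Section 16.3 opens the phone and text route to some enrolled participants, as part of the Safety Plan, "if they feel that the measures in the safety plan are ineffective and they are in impending danger of attempting suicide". They and their parents are told that a clinician will respond within 1 hour, or as soon as staff can alert one, whichever is shorter. The reason given for the possible delay is that "accredited mental health professionals and/or psychologist/psychiatrist may be providing services to other patients".

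A separate paragraph, introduced as an exception, deals with contacts "received during the night hours (e.g., after 9 pm) calls/text will not be answered until the next day". For those contacts, "they should call 911 or go to the nearest emergency room to keep themselves safe". This is the only emergency-care instruction in 16.3.

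On what families are told, 16.3 says: "Participants and their parents will be informed of such procedures in the consent and assent form".

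Section 16.7, on remote suicide risk, has its own emergency step for a participant who cannot be kept safe: "Caregiver should be contacted and directed to call 911 and/or go to the nearest Emergency Room (ER"). If the caregiver cannot be reached, staff may call 911 themselves.

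**The concern.** The route is meant for the moment when the safety plan has stopped working. As 16.3 is written, a participant in that state at 11 pm is sent to emergency care, while one in the same state at 3 pm is told to expect a call-back. The daytime instruction is therefore the weaker of the two, although the danger is the same and the section itself expects clinicians to be busy at times.

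The people concerned may be at high risk. One of the enrolment conditions in 16.4 reads "If C-SSRS yields scores of 4 or 5 or higher but parents or caregivers or adult participants state that they can keep" the participant safe at home, so ideation with intent does not in itself keep someone out of the study. Sections 12.1 and 16.3 also ask families to save the study numbers under a name that includes the word Emergency, which encourages them to call the study first. If nothing they hold says otherwise, a family could wait for the study clinician when it should be on its way to an emergency room.

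**Working it through.** No calculation applies: no sample size, error rate or event count enters the point. The check sets every passage that mentions 911, emergency care or contact hours against one situation: a participant at home, between sessions, has called the study and has not yet been called back.

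| Place | What it provides | Does it cover that situation? |
|---|---|---|
| 16.3, main paragraph | Reply within 1 hour, or sooner | States the wait; no instruction for the wait or for a missed reply |
| 16.3, night paragraph | No reply until the next day; go to 911 or an emergency room | Yes, for night contacts only |
| 16.1 (item 2) and 16.2 | Escort to the emergency department | No; in-person assessments only |
| 16.1 (item 3) | Referral to emergency care once danger is identified | No; staff must already know of the danger |
| 16.4, recommendations | Extra contact: "call and talk to participants 1 or 2 times a week as needed" | No; this contact is initiated by the study |
| 16.6 | Crisis phone and text lines | No; listed as lower-level help for C-SSRS scores 1 to 3 |
| 16.7 | Caregiver directed to 911 or an emergency room, or staff call 911 | Only once staff are in contact |
| 25.1, sample contact boxes | Phone and email details | The boxes shown have no emergency line, but they are an excerpt of the forms |

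**The wait.** The shorter of two times applies, so 1 hour is the upper limit: 1 × 60 = 60 minutes. The section gives no instruction for those 60 minutes by day, or for what follows if they pass without a reply.

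**The night window.** Its start is an example (9 pm). Its end is given only as the next day, with no clock time. A family calling at 6 am or 7 am cannot tell from 16.3 which rule applies. Weekends and holidays are not mentioned.

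**Result.** In the text available, the night caller has an emergency-care instruction. The day caller who cannot wait, or who is not called back, has none.

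**The case against.** The strongest objection is that families act on documents that could not be seen here. Section 16.3 places the route within the Safety Plan and says the procedure is explained in the consent and assent forms. Those forms, the Safety Plan template, the separate safety monitoring plan and several figures were not in the review text. A reader might infer that participants never receive a daytime 911 instruction. The documents do not support that, because the missing material may contain it. What stands is that 16.3 describes the procedure those forms are to convey, and its own wording is incomplete.

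A reader might also infer that a high C-SSRS score is accepted on a caregiver's word alone. That is too strong. Section 16.4 also lists cooperation with a Safety Plan, a named adult contact, a commitment not to attempt suicide before the next encounter, and low to moderate risk from access to means. Section 16.5 directs exclusion and referral for scores of 4 or more when safety at home or that commitment is lacking. The medical monitor and the principal investigator review safety plans after the first main interview, and the monitoring board itself advised giving out mobile numbers (25.1). These safeguards reduce the risk. None of them says what to do while a call is unanswered.

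A third tempting inference is that 12.1, which speaks of crisis contact during working hours, contradicts the 9 pm example. It need not: that sentence can be read as describing calls made by the study. It is an ambiguity at most, and the point does not rest on it.

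Finally, a call not returned within the hour is a departure from the stated procedure. That is so, but a limit set because clinicians may be busy needs a fallback. The participant who cannot wait even the permitted hour is in difficulty without any departure.

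**Conclusion.** The point holds as a gap in the wording of 16.3 and should be corrected. Participants who judge themselves in impending danger may wait up to 60 minutes by day with no emergency-care instruction in that section. The night exception that does carry one has only an example start and no end time. Section 16.7 narrows the gap, since it applies once staff are reached, but does not close it.

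The conclusion rests on the visible text and applies to the subset of participants given this route. It makes no claim about how often calls go unreturned, or that harm would follow. It is a participant-safety point and does not touch the endpoints, randomisation or analysis.

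**What to change.** In 16.3, state definite start and end times for the 1-hour call-back, including what applies at weekends and on holidays, limited to hours the clinicians already cover. Then add:

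> At any hour, if you are in immediate danger or cannot stay safe while waiting, call 911 or go to the nearest emergency room without waiting for a call-back. Do the same if your call or text is not returned within 1 hour, or if it is outside these hours.

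The any-hour sentence should come first and stand alone, so that it cannot be read as applying only outside coverage hours.

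Carry the same wording into the Safety Plan and the consent and assent forms if it is not already there. If it is, only 16.3 needs to be brought into line. Saying in 12.1 whether the working-hours remark refers to study-initiated calls is optional.

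The cost is a minor wording amendment with no added staff. The downside is that definite hours may make the stated response window narrower than families now assume.

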16.4 Suicide Risk Assessment in Person

Make sure phone numbers, email and emergency contacts are accurate and accessible.

- **C-SSRS**, ⁴⁹, all participants (particularly **scores of 4 or 5** in the C-SSRS) require: a) detailed safety planning, b) documentation of protective factors, c) psychoeducation, handling, and documentation of risk factors. (see **Access to Suicide Means**).
- **Safety Plan**, (Stanley & Brown, 2012), a safety plan with the participants and attending/present caregiver(s). **Template – uploaded in the IRB application.**
- **Protective Factors:** Caregivers/parents or legal guardians are **aware of chronically high suicide ideation (C-SSRS scores of 4 or 5)**. **Caregivers state they can keep their child safe at home despite scores of 4-5**. Document access to adult support (caregivers, teachers, extended family) and family/community support. Caregivers and participants are under the care of a psychiatrist and/or psychologist according to current standards of practice in the community. Caregivers/participants can reach mental health providers and/or know when they have their next appointment.
- **Risk Factors:** Protective factors are absent. Access to suicide means is unknown or caregivers cannot control them.

Psychoeducation and Assessment regarding Access to Suicide Means.

- Ask caregiver/participants directly about firearms, ensure weapon have been taken care of by another person in the home, store unloaded, dispose of bullets.
- Counsel participants/caregivers to dispose of excess medication. Have another person in the home (caregiver or other family members) dispense medications.
- Encourage families/caregivers to reduce the amount of alcohol stored in the home.
- Ask “what other means for hurting yourself are available in your home?”
- Involve caregivers/parents or legal guardians and extended family members and friends if possible, including those that are not living with the adolescent.

Inclusion (or re-enrollment after hospitalization/ temporary withdrawal) if:

1. **Safety Plan:** Able to cooperate with the (Stanley & Brown, 2012) Safety Plan. Additional positive criteria include details and accessibility of means and persons to enact it. Participants should be able to provide the name of an adult that they can contact if suicide ideation escalates. Additionally, participants should be able to name specific activities or de-escalating regulatory actions to cope with elevated suicide ideation. The credibility of the suicide plan is often indicated by levels of specificity and elaborations in the coping strategies provided. Evaluating a safety plan specificity is a subjective judgment, therefore the ability to cooperate to create a plan is more important than its level of detail as the latter may depend on verbal and communication skills that do not indicate willingness or ability to follow a safety plan.

2. **C-SSRS:** Any suicide ideation severity yielded by the (C-SSRS, ⁴⁹), Scores 0-5-.

Category 0 – Absent suicide ideation or attempts
 Category 1 – Wish to be Dead
 Category 2 – Non-specific Active Suicidal Thoughts
 Category 3 – Active Suicidal Ideation with Any Methods (Not Plan) without Intent to Act
 Category 4 – Active Suicidal Ideation with Some Intent to Act, without Specific Plan

Category 5 – Active Suicidal Ideation with Specific Plan and Intent
 Category 6 – Preparatory Acts or Behavior
 Category 7 – Aborted Attempt
 Category 8 – Interrupted Attempt
 Category 9 – Actual Attempt (non-fatal).
Category 10–Completed Attempt (fatal)

3. **Caregivers/parents or adult participants statement of responsibility:** If C-SSRS yields scores of 4 or 5 or higher but parents or caregivers or adult participants state that they can keep the participants safe at home.

4. **Participants statement:** Participants can commit to not attempting suicide between the present and the next research encounter.

5. **Suicide means and psychoeducation.** Low to moderate risks during evaluation of access to suicide means.

6. **Recommendation to parents** and additional measures to ensure safety of enrolled participants

- Caregiver(s) will be recommended to increase the level of care with existing providers or seek them if currently absent. Referrals to the U of M outpatient clinic will be provided to the participants and the caregiver.

- [name] (or the designated psychiatrist or accredited mental health professional) will increase contact with participants/family (call and talk to participants 1 or 2 times a week as needed), particularly if staff becomes aware of periods of high stress, family chaos, increased difficulties at school, bullying, losses, or transitions in care.

- **Document:** risk and protective factors assessment, safety plans, rationale for level of intervention/care.
- When in doubt – consult [name] or the designated pediatric psychiatrist.
- Consult with other providers in the department of psychiatry

7. The Dialectical Behavioral Therapy (DBT: [contact]) team can be consulted via email 2 weeks before the visit with copy to the PI: [contact]

16.5 Exclusion and triage of in person suicide risks. Risk factors are cumulative, the presence of one risk factor does not automatically exclude a participant. The presence of many risk factors and the absence of protective factors, however, merits considering exclusion from the research.

Exclusion and referral for increased outpatient level of care or emergency department (ED) assessment for hospitalization if:

- Scores of **4 or 5** or higher in the C-SSRS (Category 4 - 6) and:
 - **Caregivers are unable or unwilling to keep the participants safe at home.**
 - Participants show uncertainty (i.e., cannot promise not to attempt suicide) about not attempting suicide between the present and the next research session.
- Inability to fashion a credible Stanley & Brown Safety Plan.

[figure not shown]
- Determination of high chronic or acute risk due to presence of multiple risk factors and absence of protective factors: e.g., access to suicide means and unreliable or absent control over them.
- In consultation with the “on call” PI or pediatric psychologist this could result in referral for increased levels of current established care or escorting the participants and family to the emergency department (ED) at the U of M.
- Personnel will be trained to conduct and document a safety plan and interview. **The IMM and the PI will review the safety plans after the conclusion of the 1st main interview.**

[figure not shown]

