14.1 Withdrawal Circumstances:

1st High risks of imminent suicide attempts, with intent, a plan and/or other conditions for study enrollment are not met. Participants can re-enroll in the study after hospitalization and/or increased levels of care in outpatient treatment and/or environmental changes (e.g., changes in school or place of residence) that leads to demonstrable stabilization and/or decrease high acute/chronic suicide risks. To re-enroll the **PI and the IMM (with possible third opinion of Pediatric Psychiatrist if needed)** must agree on the results of the study enrollment/re-enrollment conditions.

2nd Onset of significant psychotic symptoms that clearly impair judgment and ability to assent (e.g., presence of pervasive psychotic mood, visual or auditory hallucinations or other manifestations of disorganized thoughts and judgement). Note: mild, transient psychotic symptoms are allowed within the context of a depressive episode or other diagnostic category, if they do not impair the participant's ability to assent or meet criteria for a full psychotic episode as defined by the K-SADS.

3rd Onset of neurological or metabolic illness known to significantly affect brain function and structure.

4th Onset of substance dependency disorder or new evidence that symptoms are linked to substance use.

5th Onset of claustrophobia resulting in intense discomfort in the scanner that cannot be assuaged with brief anxiety decreasing interventions (e.g., talking to the experimenter/breathing and increasing verbal contact with experimenters between pulses of the scanner).

6th Known or strongly suspected SARS-COVID-2 diagnosis in the family or household or recent (1-3 days) onset of symptoms linked to a contagious illness.

7th Medication related toxicity will result in temporary withdrawal until stabilization of symptoms is ascertained via K-SADS guided assessments and/or improvement is ascertained by their attending physician.

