16.1 Foreseeable Risks

1. **Suicide attempt or completion risk.** Because the focus of this study is an intervention for **participants with recent suicide attempts and current suicide ideation**, the participants are at increased risk for suicide attempts, increased suicide thoughts and hospitalizations. **Participants who have attempted suicide are more likely to repeat attempts, to be hospitalized or to complete suicide compared to the general population of psychiatric patients. It is highly likely that the present study will entail reporting suicide attempts, suicide completions and hospitalizations given the population we are studying. Suicide attempts, completions or hospitalizations are thus a characteristic of the population and not a likely consequence of the proposed intervention which is of minimal risk and intrusiveness.**

2. In person suicide risk will be assessed at baseline and at the post-intervention assessment and additional precautions will be taken to help ensure participant safety. The PI ([name], PhD, L.P.) will work in conjunction with a designated pediatric psychiatrist at the Department of Psychiatry Child and Adolescent Clinic. [name] or the designated pediatric psychiatrist (if the PI is on vacation or in a conference) will be available to the PI and study staff during each of the clinical assessments, to consult with the study staff regarding the suicide risk, triage, and intervention planning. In addition to these resources, the UMN outpatient clinic has a list of 6 qualified providers that experimenters can call in case of emergency. During in-person assessments, if a 72-hour hold is warranted to ensure participants safety, security personnel are readily available in case experimenters determine that there is urgent need for escorting participants and families to the emergency department (ED) for possible hospitalization and/or further evaluation.

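### The C-SSRS ranges in sections 16.4 and 16.5 contradict each other above category 5, so how preparatory acts and new attempts are handled depends on which words are read

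*Combined protocol and SAP*

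**What the plan says.** Table 2 excludes for high acute, imminent risk and refers to the Suicide Risk Assessment section for the criteria. Sections 16.4 and 16.5 are therefore the operative rule.

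- **Scale (16.4).** The printed list runs from 0 to 10. Categories 1-5 are rising ideation, with 5 being ideation with a plan and intent. Then come 6 preparatory acts, 7 aborted attempt, 8 interrupted attempt, 9 actual non-fatal attempt and 10 fatal attempt.
- **Inclusion or re-enrolment, item 2 (16.4).** "Any suicide ideation severity yielded by the" C-SSRS is accepted, with the range given as 0-5.
- **Item 3 (16.4).** "If C-SSRS yields scores of 4 or 5 or higher but parents or caregivers or adult participants state" that the participant can be kept safe at home.
- **Item 4 (16.4).** "Participants can commit to not attempting suicide between the present and the next research encounter".
- **Exclusion (16.5).** Scores of 4 or 5 "or higher in the C-SSRS (Category 4 - 6) and", followed by two sub-bullets. The first is "Caregivers are unable or unwilling to keep the participants safe at home"; the second is a participant who cannot promise not to attempt before the next session.
- **Withdrawal (14.1).** "High risks of imminent suicide attempts, with intent, a plan and/or other conditions for study enrollment are not met". No C-SSRS score is named.
- **Section 10.** Acutely suicidal participants are described as having a clear plan and also being unable to commit.
- **Timing.** Section 16.1, item 2: "In person suicide risk will be assessed at baseline and at the post-intervention assessment". Table 1 and the study-item list in section 5.1 schedule the C-SSRS at Visits 1, 4 and 5 and at optional contacts, but not at scan Visits 2 and 3.

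**The concern.** Three ranges (0-5, 4 upward, 4-6) sit on one scale within two adjacent sections. They differ at the categories that describe suicidal behaviour rather than ideation. The target participant in section 8.1 is a first-time attempter, and Table 2 accepts an attempt in the last year or at any time in life. No look-back period accompanies the score rules, so it is undefined whether the qualifying attempt itself counts as category 9.

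Two things are at stake. The first is safety: staff applying the words as printed can reach different answers for the participants at highest risk. The second is the composition of the sample. The C-SSRS is among the R33 primary outcomes (section 3.1) and the H2.2 outcomes (section 18). The data integrity paragraph of section 18 also counts a specific ideation threshold on the SIQ and C-SSRS as a mark of rigour, but the text does not yield a single C-SSRS rule.

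**Working it through.** The plan gives no figure to reproduce, so the check is an enumeration of the written rules.

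**Inputs.** C-SSRS category 0-9 (10 is fatal), caregiver or adult participant states safety at home (yes/no), participant commits (yes/no): 10 × 2 × 2 = 40 profiles. The safety plan and access to means are held favourable. Categories 4-9 account for 6 × 4 = 24 of these.

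**Step 1: inclusion items 2 and 3.** If items 2, 3 and 4 must all hold, inclusion stops at category 5. If item 3 governs, there is no cap. The two readings differ for categories 6, 7, 8 and 9 with safety stated and commitment given: 4 profiles.

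**Step 2: the two halves of the 16.5 line.** The open-ended half covers 4-9 and the bracket covers 4-6, so they differ at 7, 8 and 9. If either sub-bullet is enough, 3 of the 4 caregiver/commitment combinations trigger exclusion, and 3 × 3 = 9 profiles change status. If both are needed, 3 × 1 = 3 do.

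**Step 3: profiles at category 4 or above that are neither included nor excluded** (24 minus included minus excluded).

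| Inclusion reading | Exclusion range | One sub-bullet enough | Both needed |
|---|---|---|---|
| Capped at 5 (2 included) | 4 and above | 24 − 2 − 18 = 4 | 24 − 2 − 6 = 16 |
| Capped at 5 (2 included) | 4-6 | 24 − 2 − 9 = 13 | 24 − 2 − 3 = 19 |
| No cap (6 included) | 4 and above | 24 − 6 − 18 = 0 | 24 − 6 − 6 = 12 |
| No cap (6 included) | 4-6 | 24 − 6 − 9 = 9 | 24 − 6 − 3 = 15 |

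**Step 4: profiles both included by items 2-4 and excluded by the 16.5 C-SSRS bullet.** There are 0 of 40 under all 8 combinations, because the two sub-bullets are the complements of items 3 and 4.

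**Step 5: withdrawal.** Section 14.1 names no score. One included profile, category 5 with safety stated and commitment given, has the plan and intent that 14.1 mentions. It meets 14.1 only if imminent risk is also judged high. Section 14.1 can also be read as withdrawing anyone who no longer meets enrolment conditions. On that reading the contradiction between items 2 and 3 carries over into withdrawal.

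**Step 6: timing, a separate matter.** The item 4 commitment spans one gap between encounters. Visits 1 and 4 are three gaps apart. If each gap is the two to three weeks that section 5 says can pass, scheduled C-SSRS assessments are 3 × 2 = 6 to 3 × 3 = 9 weeks apart. This is illustrative only: section 5 also places assessments about two weeks before and after training, and the note to Table 1 allows several weeks between visits.

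**The case against.** The strongest defence is that the inclusion and exclusion rules are built as complements, so the overlap at scores 4 and 5 is deliberate and is settled by the caregiver and commitment conditions. That stands. A reader might infer that the same participant can be admitted by 16.4 and shut out by the 16.5 C-SSRS bullet. Step 4 shows that this does not occur under any reading.

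A reader might also infer that withdrawal uses yet another C-SSRS range, or that category 5 is admitted and withdrawn at once. Section 14.1 states no range, and 16.4 itself speaks of chronically high ideation at 4 or 5 as something that can be managed at home. The fault is only that 14.1 and section 10 are not tied to the scale.

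Item 2 speaks of ideation, so it may not have been meant to cap past behaviour. That is a fair reading. However, the list printed beneath it numbers ideation and behaviour on one scale, and item 3 continues upward on that scale.

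There are other safeguards. The remaining 16.5 bullets, Table 2 and the temporary withdrawal after hospitalisation for an attempt could catch a participant at 7-9. The medical monitor reviews C-SSRS items to confirm eligibility, and staff are told to consult when in doubt. These reduce the practical risk, but they work through judgement and do not remove the contradiction.

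On timing, the SIQ is given at both scan visits, the MSSI is available as needed at every visit, and the C-SSRS is repeated when an imminent attempt is suspected (16.2). The gap is therefore partly covered, and it does not cause the conflict in the ranges.

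Finally, figures in 16.5, Figure 1 and the separate safety monitoring plan were not available for this review. They may settle the and/or question, but they would not make the printed ranges agree.

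**Conclusion.** Wrong as written, within limits. Items 2 and 3 of the inclusion list disagree for categories 6-9, and the 16.5 line contradicts itself for categories 7-9. The joiner between its two sub-bullets is unstated. So is the treatment of the qualifying past attempt. Depending on the reading, 0 to 19 of the 24 profiles at category 4 or above are left without a decision.

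These are counts of rule combinations, not of expected participants; the documents give no distribution of C-SSRS scores. They assume that the safety plan and access to means are favourable and that the listed items are applied literally. The documents support neither simultaneous inclusion and exclusion nor a separate C-SSRS range for withdrawal. The mismatch between the item 4 commitment and the C-SSRS schedule is a separate and partly mitigated monitoring point.

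**What to change.** The investigators, with the medical monitor and the DSMB, should reconcile section 10, 14.1, 16.1 item 2, 16.4 items 2-4, 16.5, Table 1 and the study-item list in one amendment, so that:

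1. the C-SSRS ranges stated in 16.4 and 16.5 agree with each other and with the printed scale;
2. 16.5 says explicitly whether one or both sub-conditions are required;
3. the qualifying past attempt is unambiguously distinguished from new behaviour;
4. the wording of 14.1 and section 10 is tied to the same definitions;
5. the visits at which the item 4 commitment is checked match the period it is stated to cover.

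Which thresholds and clinical rules apply is for those groups to decide; none is proposed here. The cost is one protocol amendment and staff retraining on the reconciled text. Any added work at the scan visits depends on how they resolve the fifth item.
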